A summary of substance use will be provided by treatment group and total.

- **Medical Conditions and Concomitant Medications**

Current/Past Medical Conditions

The number and percentage of subjects with current and past medical conditions recorded in eCRF will be provided by treatment group and total.

Concomitant Medications

The number and percentage of subjects reporting the use of each concomitant medication will be summarized by treatment group and total by anatomical therapeutic chemical (ATC) Level 1, and Ingredient. Summaries for pre-therapy, on-therapy, and post-therapy medication will be provided separately. See Section 15.4.1 for the study phases.

Other Concomitant Medications (On-Therapy ESA, iron, and anti-hypertensive medication)

The similar summary as above will be provided by treatment group and total focusing on on-therapy ESA, on-therapy iron medication (see Section 15.6.2), and on-therapy anti-hypertensive medications. See Section 15.4.1 for the study phases.

Blood Products and Blood Supportive Care Products (On-Therapy)

The number and percentage of subjects who use blood products and/or blood supportive care products will be provided by treatment group and total. The details for the use will also be summarized.

- **Exposure and Treatment Compliance**

Exposure to Study Treatment

Full details of exposure definition are presented in Section 15.6.2.

Time on study treatment (days), subject daily dose (for daprodustat) or monthly dose (for epoetin beta pegol), and cumulative dose will be summarized using the number of subjects exposed, mean, standard deviation, median, minimum, and maximum by treatment groups. Time on study treatment will be categorized in different time periods (< 3 months, 3 months to 6 months, >6 months to 12 months, >12 months; 1 month = 30.4375 days) and the number and percentage of subjects exposed will be displayed for each category.

Treatment Compliance

Full details of treatment compliance definition are presented in Section 15.6.2.

The number and percentage of subjects within each category will be summarized by treatment groups and total for up to Week 4, Week 40 to 52, and overall. Up to Week 2 and Week 2 to 4 will also be summarized for only cohort 3. The categories will be classified into under compliant, compliant, over compliant.

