Period for Compliance Calculation	Dosing Start Date	Dosing Stop Date ^[2]
0 – 2 Week ^[1]	Treatment Start Date	Day 1 Dosing Stop Date
0 – 4 Week (Cohort 1)	Treatment Start Date	Day 1 Dosing Stop Date
0 – 4 Week (Cohort 3)	Treatment Start Date Week 2 Dosing Start Date	Day 1 Dosing Stop Date Week 2 Dosing Stop Date
2 – 4 Week ^[1]	Week 2 Dosing Start Date	Week 2 Dosing Stop Date
Primary Efficacy Evaluation Period (40 – 52 Week)	Dosing Start Date at each visit from Week 40 to 48	Dosing Stop Date at each visit from Week 40 to 48
Overall	Dosing Start Date at each visit	Dosing Stop Date at each visit

[1] Compliance will not be calculated for Cohort 1.
 
[2] If Dosing Stop Date is missing Treatment Stop Date will be used.
		
Treatment Compliance of Epoetin Beta Pegol		

 ● Treatment compliance of epoetin beta pegol will be based on dosing records (dose per every 2 or 4weeks are captured) and categorized as Under compliance, Compliant, and Over Compliant 
 ○ Calculated compliance < 80% → Under Compliant ○ Calculated compliance ≥ 80% and ≤ 120% → Compliant ○ Calculated compliance > 120% → Over Compliant ● Calculated compliance will be provided to derive compliance category only, not provided for any displays. It will be carried using the following formula: 
 ○ Calculated Compliance (%) = [(Total # of dosing) / (Total # of planned dosing)] x 100 ○ Total # of dosing = Sum of Numbers of dosing records where Prescribed Dose equals Actual Dose ○ Total # of planned dosing = Sum of # of planned dosing of each dosing records ○ # of planned dosing = Duration / 14 (if Frequency = every 2 weeks and Prescribed dose ≠ 0) Duration / 28 (if Frequency = every 4 weeks or Prescribed dose = 0) ○ Duration = Start Date of next dosing record – Start Date 
 ▪ If next dosing record is missing, Treatment Stop Date (see Section 15.6.1)+ 1 day will be 		

Exposure	
used. instead of Start Date of next dosing record.	

 Dosing records included in compliance calculation for each period are as below. 	
Period for Compliance Calculation	Dosing Records
0 – 2 Week ^[1]	First record of Day 1
0 – 4 Week	Day 1 to Week 2 (Day 1 for ESA users in Cohort 1)
2 – 4 Week ^[1]	Day 1 (ESA users) Week 2 (ESA non-users)
Primary Efficacy Evaluation Period (40 – 52 Week)	Week 40 to 48
Overall	All records

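### Epoetin compliance for Weeks 0-2 and 2-4 can mislabel a fully dosed ESA non-user on every-2-week dosing when visits fall at the window edges

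*SAP*

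**What the plan says.** SAP Section 15.6.2 (Treatment Compliance of Epoetin Beta Pegol) defines compliance as doses given over doses planned.

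- Numerator: "Total # of dosing = Sum of Numbers of dosing records where Prescribed Dose equals Actual Dose".
- Denominator: for every-2-week records with a non-zero prescribed dose, "of planned dosing = Duration / 14"; otherwise "Duration / 28 (if Frequency = every 4 weeks or Prescribed dose = 0".
- Elapsed time: "Duration = Start Date of next dosing record – Start Date". If there is no next record, the Treatment Stop Date plus one day is used.
- Categories: "Calculated compliance < 80% → Under Compliant" and "Calculated compliance > 120% → Over Compliant"; anything between is compliant.

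The Weeks 0-2 calculation uses one record ("First record of Day 1"). The Weeks 2-4 calculation uses the Week 2 record for ESA non-users and the Day 1 record again for ESA users. Section 6.2 puts both periods into the compliance summary: "Up to Week 2 and Week 2 to 4 will also be summarized for only cohort 3". The schedule in Appendix 2 (Section 15.2.1) permits ±3 days at Week 2 and at Week 4, and ±5 days from Week 8 to Week 52.

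**The concern.** A whole-number numerator is set against a denominator that moves with the calendar. Over a long period the visit-day scatter is small relative to the total. Over a single two-week interval it is not: a few permitted days early or late can move the ratio past 80% or 120% although the one planned injection was given as prescribed.

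Daprodustat compliance does not behave this way. Its planned tablets are the days of dosing times the tablets per day, so an early or late visit changes tablets taken and tablets planned together. The artefact can therefore arise in one arm only, within a table that sets the arms side by side. Section 15.6.2 also says that the epoetin percentage serves only to derive the category and is not displayed, so a reader of the table could not see that an over-compliant label came from an 11-day interval after one correct injection.

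**Working it through.** The SAP gives no worked epoetin compliance figure to reproduce. As a check on the formula, a nominal 14-day interval gives 1 / (14/14) = 100%. So does the withdrawal rule in Section 15.6.1: last dose + 13 days, then + 1 day, is 14 days.

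**Limits in days.** With one dose, compliance = 100 × 14 / d, where d is the interval in days.
- Over compliant if d < 14 / 1.2 = 11.67 days.
- Under compliant if d > 14 / 0.8 = 17.5 days.

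**Weeks 0-2, every-2-week dosing.** Day 1 to Week 2 ± 3 days gives d = 11 to 17.

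| d | 11 | 12 | 13 | 14 | 15 | 16 | 17 |
|---|---|---|---|---|---|---|---|
| % | 127.3 | 116.7 | 107.7 | 100.0 | 93.3 | 87.5 | 82.4 |

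Only d = 11 is misclassed, as over. Under-compliance cannot arise.

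**Weeks 2-4, every-2-week dosing.** Assume injections on the visit day and both windows counted from Day 1. Then d = 14 + b − a, with a and b each from −3 to +3, so d = 8 to 20.

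| d | 8 | 9 | 10 | 11 | 12-17 | 18 | 19 | 20 |
|---|---|---|---|---|---|---|---|---|
| % | 175.0 | 155.6 | 140.0 | 127.3 | 116.7-82.4 | 77.8 | 73.7 | 70.0 |
| Label | over | over | over | over | compliant | under | under | under |

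Of the 7 × 7 = 49 pairs of permitted visit days, 4 + 3 + 2 + 1 = 10 are over, 3 + 2 + 1 = 6 are under and 33 are compliant. If Week 4 were counted from the Week 2 visit instead, d would run from 11 to 17 and only the 11-day case would remain.

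**Share mislabelled among fully dosed subjects.** The SAP gives no distribution of visit days, so these are illustrations.
- Visits uniform over the window: 1/7 = 14% in Weeks 0-2 and 16/49 = 33% in Weeks 2-4.
- Discretised normal over the window, SD 1.5 days: 3.7% and 14.4%.

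**Where the rule works.**
- ESA users, one dose over 25-31 days with divisor 28: 28/25 = 112.0% to 28/31 = 90.3%.
- Weeks 0-4, two doses on every-2-week dosing: 2 × 14 / 25 = 112.0% to 2 × 14 / 31 = 90.3%.
- Weeks 40-52, three every-4-week doses: Week 40 to Week 52 spans 84 ± 10 = 74-94 days. The last record runs to the Treatment Stop Date + 1, and for completers that stop date is the Week 52 visit, so the duration is 75-95 days: 3 × 28 / 75 = 112.0% to 3 × 28 / 95 = 88.4%.

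All of these are always compliant.

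**The case against.** The best defence is that doses given over doses expected for the time elapsed is a coherent measure of dosing rate. It flags compressed or stretched intervals, which a simple one-of-one count cannot see. That stands as a real cost of the fix. It does not rescue the label: someone given exactly one prescribed dose at a permitted visit has not been over-dosed by count, and the table does not say that it reports a rate.

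It can also be said that the 8-20-day range is not given in the SAP. That is correct. The footnotes to the schedule are not shown, dosing detail is left to the protocol, and the range rests on the two assumptions above. The 11-day case in Weeks 0-2 needs only the first of them, that injections fall on visit days.

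Three stronger readings are tempting and not supported.
- That fully dosed epoetin subjects are generally mislabelled: intervals of 12-17 days are classed correctly, and division by 14 applies only to every-2-week dosing.
- That both errors occur in both periods: under-compliance needs at least 18 days, which is outside the Weeks 0-2 range.
- That the per-protocol population or the efficacy results are affected: exclusion 08 in Appendix 1 uses only the primary efficacy evaluation period, where the rule works.

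Finally, the consequence is small. The Weeks 0-4 row for the same subjects, in the same table, is right.

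**Conclusion.** The concern holds as a minor defect. For epoetin ESA non-users on every-2-week dosing in Cohort 3, the short-period rule can label a fully dosed subject over compliant at 11 days in Weeks 0-2, and over compliant at 8-11 days or under compliant at 18-20 days in Weeks 2-4. The Weeks 2-4 range depends on injections being given on visit days and on both windows being counted from Day 1. How many subjects would be affected cannot be derived, because the SAP gives neither the visit-day distribution nor the number of such subjects.

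The effect is a possible artificial difference between arms in two rows of the descriptive compliance table, and in the matching listing so far as it carries the epoetin category; the Section 6.1 note mentions these periods in the listing only for daprodustat. No analysis population or efficacy or safety analysis in the SAP depends on these two categories.

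**What to change.** In Section 15.6.2, for the 0-2 and 2-4 week periods only, and only for every-2-week dosing records with a non-zero prescribed dose, set the number of planned doses to the number of injections scheduled in the period (one per record) in place of elapsed days over 14. Leave the every-4-week, zero-dose and longer-period rules as they are. The restriction matters: ESA users have no injection scheduled at Week 2, so a blanket count of one for each short period would not fit them.

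A fully dosed subject then scores 1/1 = 100% at every permitted interval, and a dose that differs from the prescribed one scores 0/1 = 0%. The wording should tie the count to the schedule, so that a scheduled injection that was missed and left no record still counts as planned.

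The cost is a short wording change and a small change to the derivation program, with no new data. The downside is that these two rows would no longer flag compressed or stretched dosing intervals.

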15.6.3. Efficacy

Hgb Values
Central laboratory and HemoCue Hgb Values

 For reporting purposes, central laboratory Hgb values will be used, unless otherwise specified. However, if a central laboratory Hgb value is missing, a corresponding non-missing HemoCue Hgb value, which is associated with the identical subject number and visit, will be used.
Evaluable Hgb Values

 It will be used for reporting sensitivity analysis results and Hgb listings. Evaluable Hgb values will be based on on-therapy central laboratory and/or HemoCue Hgb values that are not taken within the 8 weeks following a red blood cell transfusion, a whole blood transfusion, or a non-randomized ESA medication which occurs on or after the randomization date (except protocol-specified ESA treatment in screening period). 
If an Hgb record meets at least one following criteria, the Hgb record will be regarded as non-evaluable.
 
 Blood Product Administration Date < Date of Hgb data ≤ Blood Product Administration Date + 56 (days) ESA Start Date < Date of Hgb data ≤ ESA Stop Date + 56 (days)

Hgb Values

Flowchart for Hgb analyses

- This flowchart will be applicable, unless otherwise specified
 - Basically, scheduled visits between Day 1 and Week 52 will be applicable to this flowchart, but analyses including by-visit summaries may include other scheduled visits (ie. screening and follow-up visit).
- [1] Regarding partially evaluated Hgb values, the following summaries of Hgb will include unscheduled visits:
- Summary of Time (weeks and %) within Hgb target range during the primary efficacy evaluation period
 - Summary of Number (%) of subjects who have an Hgb level of less than 7.5 g/dL
 - Summary of Number (%) of subjects who have an Hgb level of more than 13.0 g/dL and number of episodes
 - Time (in days) to reach the lower Hgb target (11.0 g/dL)

Hgb increase of more than 2.0 g/dL over any 4 weeks

- For this reporting purpose, Hgb values from central laboratory will be used as previously described.
- A subject who has at least one record with Hgb increase of more than 2.0 g/dL over any 4 weeks will be counted and all episodes will be listed.
- Hgb increase will be calculated for scheduled visits between Day 1 and Week 52 if available (i.e. Week 4 Hgb - Day 1 Hgb, Week 8 Hgb - Week 4 Hgb, ...)

Illustration of calculation (example in case of Week 12 missing, until Week 24 visit)

Hgb (g/dL)	Lab Date	Study Day	Visit	Hgb increase
9.1	PPD	1	Day 1	Not calculated
9.8		30	Week 4	0.7
11.9		61	Week 8	2.1
12.6		127	Week 16	Not calculated
12.7		158	Week 20	0.1
12.3		183	Week 24	-0.4

- Odds ratio and its 95% CI will be obtained using the same statistical model described in Section 7.2.5.
- When the odds ratio is undefined, it will not be presented.

Scatter plot of Hgb assessments: Central Laboratory vs. HemoCue

- All available pairs of Hgb (i.e. non-missing values in both from central laboratory and from the corresponding HemoCue measurement) will be used, regardless of treatment groups and visits. The figure will include a linear regression line with 95% CI band, R-squared, and Pearson's correlation coefficient.

Hgb Values
Scatter plot of Change from Baseline in Hgb at Week 4 vs covariates of interest

 The following scatter plot figures will be produced separately: 
 Change from baseline in Hgb (g/dL) at Week 4 vs. Baseline body weight (kg) Change from baseline in Hgb (g/dL) at Week 4 vs. Baseline Hgb (g/dL) Change from baseline in Hgb (g/dL) at Week 4 vs. Prior ESA dose Different displays by prior ESA use will be used to differentiate them. Vertical axis will indicate the change from baseline in Hgb (g/dL) at Week 4, horizontal axis will indicate the covariates of interest, baseline body weight (kg), baseline Hgb (g/dL), or prior ESA dose (IU/week). Only individual plots will be provided unlike the scatter plot of Hgb assessments.
Scatter plot of Mean Dose during Week 40 to 52 vs. Covariates of Interest

 The following scatter plot figures will be produced for overall: 
 Mean Dose during Week 40 to 52 vs. Baseline Body Weight (kg) Mean Dose during Week 40 to 52 vs. Baseline Hgb Mean Dose during Week 40 to 52 vs. Prior ESA dose Different displays by prior ESA use will be used to differentiate them. Vertical axis will indicate the mean dose (mg), horizontal axis will indicate the covariates of interest; baseline body weight (kg), baseline Hgb (g/dL), or prior ESA dose (IU/week). Mean dose will be calculated from the arithmetic mean using the latest 3 exposure records (i.e., for completers Week 40, 44, and 48), which are based on the actual doses and the scheduled visits. Subjects who has less than 3 dosing records will be excluded from the figures. Mean dose during Week 40 to 52 will also be summarized and listed. Only individual plots will be provided unlike the scatter plot of Hgb assessments.

Time in Target Range																																			
Time (weeks and percentage) in Target Range During the Primary Efficacy Evaluation Period																																			

 For this reporting purpose, on-therapy Hgb values of central laboratory during Week 40 to Week 52, including unscheduled visits, will be used. However, if a central laboratory Hgb value is missing, a corresponding non-missing HemoCue Hgb value, which is associated with the identical subject number and visit, will be used. Number of days that a subject's Hgb is within the analysis range of 11.0-13.0 g/dL inclusive between Week 40 and 52, including any on-therapy Hgb values that were taken during this time period. Linear interpolation is used to estimate Hgb between visits, if a subject has an intermittent missing value (Rosendaal1993). 																																			
Illustration of calculation																																			

  
 Hgb (g/dL)	Lab Date	Visit	Ref Day	Hgb Shift	Total shift (%) within range	Time in range (weeks)	
   
 9.9	PPD	Week 40	0	NC	NC	NC	
 
 11.2		Week 44	31	1.3 (=11.2-9.9)	total shift: 0.2 0.2/1.3=15.38%	(31-0)*0.1538/7 =4.77/7 (weeks)	
 
 missing		Week 48	61	NA	NA	NC	
 
 13.4		Week 52	92	2.2(=13.4-11.2)	total shift: 1.8 1.8/2.2=81.82%	(92-31)*0.8182/7 =49.91/7 (weeks)	
  
	Hgb (g/dL)	Lab Date	Visit	Ref Day	Hgb Shift	Total shift (%) within range	Time in range (weeks)	9.9	PPD	Week 40	0	NC	NC	NC	11.2		Week 44	31	1.3 (=11.2-9.9)	total shift: 0.2 0.2/1.3=15.38%	(31-0)*0.1538/7 =4.77/7 (weeks)	missing		Week 48	61	NA	NA	NC	13.4		Week 52	92	2.2(=13.4-11.2)	total shift: 1.8 1.8/2.2=81.82%	(92-31)*0.8182/7 =49.91/7 (weeks)
Hgb (g/dL)	Lab Date	Visit	Ref Day	Hgb Shift	Total shift (%) within range	Time in range (weeks)																													
9.9	PPD	Week 40	0	NC	NC	NC																													
11.2		Week 44	31	1.3 (=11.2-9.9)	total shift: 0.2 0.2/1.3=15.38%	(31-0)*0.1538/7 =4.77/7 (weeks)																													
missing		Week 48	61	NA	NA	NC																													
13.4		Week 52	92	2.2(=13.4-11.2)	total shift: 1.8 1.8/2.2=81.82%	(92-31)*0.8182/7 =49.91/7 (weeks)																													

Time in Target Range

Overall time in range = $(4.77 + 49.91)/7 = 54.68/7 = 7.81$ (weeks) Percent time in range = $7.81/(92/7) = 59.42\%$


NC: Not calculated, NA: Not available
 
 • Hgb laboratory assessment date will be used to calculate a duration (Ref Day) between assessments. 
 ○ Duration between assessments = [Hgb lab date] – [Hgb lab date of the previous measurement] 
If a subject has withdrawn from the treatment before Week 40 the duration between Week 40 to Week 52 cannot be calculated, the subject will not be included in a summary.
 
Basically, the duration should be [Week 52 lab date – Week 40 lab date] unless a subject has withdrawn before Week 52. In the case of withdraw before Week 52, Treatment Stop Date (see Section 15.6.1) will be used instead of Week 52.
 
 • As an above example, suppose a subject has Hgb reading 9.9 g/dL on August 1st (Week 40), then reading if 11.2 g/dL on September 1st. The assumption is made that the week, between these scheduled assessments the subjects Hgb increases from 9.9 to 11.2 g/dL in a linear manner, To following steps are taken to calculate the time (days) the subject’s Hgb was within target range (11.0 to 13.0 g/dL). 
 1. Calculate amount of Hgb shift (9.9 to 11.2 = 1.3 shift) and Hgb shift within range (0.2 out of shift is within range of 11.0 – 13.0) 2. Calculate percent of total shift (%) within range (0.2/1.3 = 15.38%) 3. Estimate the number of weeks since last visit within range (15.38% x duration between assessments = 15.38% x 31/7 weeks = 0.68 weeks within range) 
If a subject has an intermittent missing Hgb assessment (on-therapy), the linear interpolation will be done by ignoring missing Hgb data.
 
To calculate overall time (weeks) in Hgb target range, the total days in range for each time period are added together and divided by 7.
 
The % of time in range between Week 40 and Week 52 for a subject will be calculated by calculating overall time (weeks) within range and dividing by the total duration (weeks) between Week 40 to Week 52. Similarly, the % of time above Hgb target range and % of time above and below Hgb target range will be calculated,

Time (days) to reach the lower Hgb target (11.0 g/dL)

 • Time to reach the lower Hgb target will be determined as follows: 
 ○ Time to reach the lower Hgb target = Date to reach the lower Hgb target – Randomization Date + 1 day • Subjects who could not reach the lower Hgb target during on-therapy will be regarded as censored. Censored time will be determined as follows: 
 ○ Censored time = Treatment Stop Date – Randomization Date + 1
Dose Adjustment
Dose adjustment algorithm

 • Dose Adjustment algorithm will be based on HemoCue Hgb values at scheduled visits. No Hgb values measured at unscheduled visits will be included. • Dose will be derived from actual dose. • The following table illustrates the algorithm using analysis flags as below: 
 ○ (FL_A): Adjustment flags will be counted if actual dose is changed from that of the previous visit.

Dose Adjustment

- (FL_B): Over 13 g/dL flags will be counted if HemoCue Hgb >13 g/dL is observed.
 - (FL_C): Interruption flags will be counted if actual dose is zero.
- Treatment durations in each visit will be calculated based on the following formula:
- Daprodustat
Duration (days) = Treatment Stop Date in the visit – Treatment Start Date in the visit + 1 day
 - Epoetin beta pegol group
Treatment stop date in the visit will be derived from [treatment start date in the next visit – 1 day]. If there is no record of the next scheduled visit, Treatment Stop Date (see Section 15.6.1) will be applied for the record.

Illustration of dose adjustment algorithm (24-week case)

Visit (Example)	Treatment Start date/ Stop date	Duration	HemoCue Hgb (g/dL)	Dose (mg)	(FL_A)	(FL_B)	(FL_C)
					Adjust-ment	Over 13 g/dL	Inter-ruption
Day 1	PPD	29	11.1	4	N	N	N
Week 4		14	11.4	4	N	N	N
Week 8		30	11.8	2	Y	N	N
Week 12		31	13.4	0	Y	Y	Y
Week 16		30	12.6	0	N	N	Y
Week 20		31	11.7	1	Y	N	N
Week 24	-	-	12.3	-	-	N	-

For programmers, note that the flags are for the purposed of illustration, and are not intended to imply any type of requirement.

- For summary tables, further details are described within the next items;
- 'Duration (days) of treatment interruption due to Hgb >13 g/dL'
 - 'Dose adjustment'
 - Number of dose adjustment to reach the lower Hgb target (11.0 g/dL)

Duration (days) of treatment interruption due to Hgb >13.0 g/dL

Calculation of duration of treatment interruption due to Hgb >13.0 g/dL will be based on the dose adjustment algorithm specified in the protocol.

- Duration (days) = Sum of [Duration]_n
where
[Duration]_n represents exposure duration at visit n to meet the following.
 - Treatment interruption is made due to HemoCue Hgb over 13 g/dL and consecutive until treatment is resumed.

In the above illustration, duration = 61 (days), from Week 12 and 16 visit records.

Dose adjustment

Calculation of frequency of dose adjustment will be based on the above algorithm.

- Number of dose adjustment will be counted for each subject as follows:
 - Counts of adjustment flag = 'Y'

Dose Adjustment
Number of dose adjustment to reach the lower Hgb target (11.0 g/dL)

 Reaching the lower Hgb target will be determined on the basis of central laboratory Hgb. Subjects who has a baseline central laboratory Hgb value within target range or who does not reach the lower Hgb target during treatment period will be excluded from the summary. Number of dose adjustment to reach the lower Hgb target will be counted for each subject as follows 
 Counts of adjustment flag = 'Y' at visits before Date to reach the lower Hgb target.

Iron Endpoints									
Oral Iron Use									

 The following iron-containing drugs will not be included in the analysis of iron use. 
 GSK drug code: 54909401 (SUCROFERRIC OXYHYDROXIDE; P-TOL). 									
Subjects who used IV and/or oral iron									

 Number of subjects who used IV and/or oral iron will be summarized Subjects who used IV and/or oral iron will be defined as follows: 
 Subjects with on-therapy IV and/or oral iron medication collected in a specific eCRF form (CONMEDS-IRON). Regarding oral iron use, the number of subjects who used ferric citrate and other than ferric citrate will also be counted respectively. 									
Oral Iron Dose by Quarter									

 Records of on-therapy iron medication will be used for the following calculations. Summary will be created for all subjects (both iron users and iron non-users) and iron users respectively. In a summary containing all subjects, iron dose of subjects who do not use iron medication will be calculated as 0 mg. Monthly average oral iron during the treatment period = Total oral iron dose (mg) during the treatment period / (duration in the treatment period (days) / 30.4375 days) Monthly average oral iron by quarter = Total oral iron dose during each quarter (mg) / (duration in a quarter (days) / 30.4375 days). Total oral iron dose during each quarter (mg) will be carried with the following formula using each record. Duration will be derived from iron medication start/stop date: 
 Total oral iron dose during each quarter (mg) = (iron dose₁*frequency₁*duration₁) + ... + (iron dose_n*frequency_n*duration_n) Duration (days) = (stop date₁ - start date₁ + 1) + ... + (stop date_n - start date_n + 1) Frequency is defined as follows: 
 If subject receives iron dose with once daily → frequency = 1 If subject receives iron dose with BID → frequency = 2 If subject receives iron dose with TID → frequency = 3 If subject receives iron dose with QID → frequency = 4 
Total oral iron dose (mg) during the treatment period will be carried in the same manner.
 
 Quarters/Duration will be defined as follows: 
  
 	Start Date	End Date	
   
 baseline	Screening Date	Randomization Date - 1	
 
 Treatment	Randomization Date	Treatment Stop Date	
  
		Start Date	End Date	baseline	Screening Date	Randomization Date - 1	Treatment	Randomization Date	Treatment Stop Date
	Start Date	End Date							
baseline	Screening Date	Randomization Date - 1							
Treatment	Randomization Date	Treatment Stop Date							

period		
Quarter 1	Randomization Date	Treatment Start Date at Week 12 - 1 day
Quarter 2	Treatment Start Date at Week 12	Treatment Start Date at Week 24 - 1 day
Quarter 3	Treatment Start Date at Week 24	Treatment Start Date at Week 40 - 1 day
Quarter 4 ^[1]	Treatment Start Date at Week 40	Treatment Stop Date

NOTES:

- A Quarter End Date will be replaced with Treatment Stop Date (see Section 15.6.1) when treatment start date at Week 12, 24, or 40 is missing (i.e. early withdrawal before Week 12, 24, or 40). In this case, the subsequent Quarter(s) will not be generated.
- Iron medication start/stop date will be defined newly for the analyses in addition to Quarter start/end date to derive amount of iron dose within a specified Quarter (analysis flags may be used to judge which quarters the iron records should belong to).

[1] Quarter 4 represents the primary efficacy evaluation period.

- If iron medication start date < screening date, the iron medication start date will be replaced with screening date for the analysis.
- If iron medication stop date > Treatment Stop Date, the iron medication stop date will be replaced with Treatment Stop Date for the analysis.
- If iron medication start date and stop date step over quarters, the iron medication record will be divided; the end date in the former of divided record and the start date in the latter of divided record will be the former quarter end date and the latter quarter start date, respectively.
- If no start or stop date is recorded on iron medication, the date will be replaced with Screening Date or Treatment Stop Date, respectively.
- For ferric citrate (trade name: Riona, GSK drug code = 00752601), iron dose value for analyses will be converted as follows,
 - Iron dose for analyses (mg) = iron dose (mg) x 62 / 250

TIBC

- TIBC will be calculated automatically by the central laboratory using:
 - $TIBC = UIBC + \text{total iron}$

TSAT

- Based on literature review the distribution of TSAT is skewed and requires a log-transformation. Calculation of statistics on log-transformed data are described in Section 5.2.
- TSAT will be calculated automatically by the central laboratory using:
 - $TSAT = 100 * (\text{Serum Iron}/TIBC)$

Hepcidin

- Based on literature review the distribution of hepcidin is skewed and requires a log-transformation. Calculation of statistics on log-transformed data are described in Section 5.2

Iron Use Subgroup

- The baseline iron use will be defined as a subject takes a pre-therapy iron medication excluding sucroferric oxhydroxide (trade name: P-TOL, GSK drug code = 54909401).

